7.2 LOST TO FOLLOW-UP

A participant will be considered lost to follow-up if: 1) he or she does not complete the end of month survey at the end of the 6-month (~180 day) home monitoring period **and** 2) study staff are unable to contact the participant after a minimum of 3 attempts.

The following actions must be taken if a participant fails to complete the end of the month survey at the end of the 6-month (~180 day) intervention period:

- The site will attempt to contact the participant and counsel the participant on the importance of completing the survey and ascertain if the participant wishes to and/or should continue in the study
- The site will make every effort to regain contact with the participant (where possible, 3 telephone calls/emails/texts and, if necessary, a certified letter to the participant's last known mailing address or local equivalent methods) before a participant is deemed lost to follow-up. These contact attempts will be documented in the participant's study file.
- Participants that continue to be unreachable will be considered to have withdrawn from the study (with a primary reason recorded as lost to follow-up).

8 STUDY ASSESSMENTS AND PROCEDURES

8.1 ENDPOINT AND OTHER NON-SAFETY ASSESSMENTS

Participants will complete a baseline assessment, daily and monthly assessments during a 6-month (~180 day) home monitoring period, and two follow-up assessments. Study data will be collected via self-report into web or app-based surveys and a consumer wearable (Fitbit®).

Eligibility and baseline procedures and assessments can be conducted either virtually via teleconference/webinar or in-person. Daily, monthly and follow-up assessments will be conducted virtually through the CareQOL app; monthly or follow-up assessments may also be conducted by interview.

8.1.1 TBI DOCUMENTATION

We will verify and document TBI status and injury severity of the care recipient for all participants. Data must conform to the TBI Model Systems classification, and be obtained from official medical documentation (e.g. medical records).

8.1.2 CARE PARTNER ELIGIBILITY

Confirmation of care partner eligibility according to criteria listed in Section 5, above, will be documented on the Eligibility CRF. It will occur prior to informed consent being obtained and before any study procedures associated with baseline assessment. Eligible individuals will then participate in the consent process, followed by randomization and baseline data collection.

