4 STUDY DESIGN

4.1 OVERALL DESIGN

Study Design: This behavioral trial will use a two-arm randomized controlled design. Each of the up to 280 care partner participants will be randomized to an active “JITAI” arm or to a control arm. The random allocation of participants to the treatment arm or control arm establishes the basis for testing the statistical significance or difference between the groups in HRQOL (caregiver strain, depression and anxiety).

Randomization: Blocked randomization will be used to limit bias and achieve an equal distribution of participants to the control and treatment arms. A randomization list will be generated for each site and the study statistician will oversee randomization. The participant will be randomized once he/she is deemed eligible and has provided informed consent (i.e. at Enrollment prior to baseline data collection). The study coordinator/research assistant who consented the participant will use their site’s randomization list to assign the participant to the correct study arm.

Duration of Study Participation: Study participation for both arms of the study (control and JITAI) involves a baseline assessment, followed by an approximate 10-day run-in period then a 6-month (180 day) home monitoring period (in which the intervention will be administered to the JITAI group). After the completion of the 6-month (180 day) home monitoring period, post-intervention surveys will be administered at 3 months (90 days) and 6 months (180 days) after the end of the 6-month (180 day) home monitoring period. Thus, the total duration of the study is ~375 days.

Study Sites: This is a multi-site study involving two sites: University of Michigan and Baylor College of Medicine. University of Michigan is the lead site and their IRBMED will serve as the single IRB for this study.

Study Intervention: The just in time adaptive intervention (JITAI) uses sensor data derived from the Fitbit® (e.g., accelerometer-based estimates of physical activity and sleep) and real-time self-report ratings (assessed once daily) of HRQOL (caregiver strain, depression, anxiety) to deliver personalized “pushes” to participants via a study specific app (CareQOL app). The personalized pushes will be delivered on ~50% of the days over the 6-month intervention period.

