5.4 SCREEN FAILURES

Screen failures are defined as participants who consent to participate in this study but are not subsequently assigned to the study intervention or entered in the study. Screen failures are unlikely in this study because eligibility assessment occurs pre-informed consent. However, if during the 10-day run-in period before the 6-month home monitoring period starts the study team is made aware of something that would change their eligibility, the participant will be noted as a screen failure.

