6.2 FIDELITY

For this study, the intervention will be administered via the CareQOL app. The study team will conduct training during the baseline visit with each participant which will include:

- Helping the participant download and register for the CareQOL and Fitbit® apps on their personal device
- Helping the participant set any relevant app settings (e.g., make sure alerts are turned on/off, privacy settings, etc.)
- Demonstrating the CareQOL app features to the participant (e.g., participant dashboard, etc.)
- Ensuring that the participant understands the importance of entering the daily ratings and wearing the Fitbit®
- Explaining the relationship between the daily ratings and Fitbit® data and the intervention prompts (JITAI group only)
- Demonstrating how to sync the Fitbit® (including using the Fitbit® app) and how to enter the daily ratings in the CareQOL app

During the 10-day run-in period between the baseline visit and the start of the intervention, study team members will assist participants to make sure that participants can:

- Successfully wear and sync the Fitbit®
- Successfully respond to the EMA prompts

Participants who are unable to successfully complete the run-in period will be terminated from the study and noted as a screen failure.

Training and training materials will be provided to all study team members. New study members will undergo training before the study is started. Training will be documented in the electronic regulatory binder.

Participant adherence to the protocol will be assessed throughout the study. Study staff will have access to the CareQOL app dashboard which can be used to monitor participant engagement and adherence with the app. Specifically, study staff will monitor:

- Adherence to EMA entry
- Adherence to Fitbit® use/syncing
- Adherence to completing the end of month surveys (~30, 60, 90, 120, 150, 180 day)
- Adherence to completing the 3-month (~270 days) and 6-month (~360 days) post-intervention surveys

Adherence will be calculated as a percentage for each of these areas for all participants who are not withdrawn or lost to follow-up.

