8.1.5.1 BASELINE ASSESSMENTS

Participants will be prompted by the CareQOL after registration to complete the baseline HRQOL assessments. Administration time is 10-15 minutes.

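### Baseline strain, anxiety and depression are collected after randomisation with no blinding described, so the reference for every change score may be affected by knowledge of the arm

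*Combined protocol and SAP*

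**What the plan says.** Two sections fix the sequence. Section 8.1.2 states: "Eligible individuals will then participate in the consent process, followed by randomization and baseline data collection". Section 4.1 times randomisation the same way ("i.e. at Enrollment prior to baseline data collection"). Site staff apply the allocation: "The study coordinator/research assistant who consented the participant will use their" site list to place the person in an arm. No blinding of participants or staff is described.

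Section 6.2 puts training in the baseline visit. Registering for the app is one item, for everyone. Another is for one arm: "Explaining the relationship between the daily ratings and Fitbit® data and the intervention prompts (JITAI group only". The staff who deliver that item must know the arm. Section 8.1.5.1 adds: "Participants will be prompted by the CareQOL after registration to complete the baseline HRQOL assessments". No section says whether the arm-specific item comes before or after the survey, or when the participant is told the arm.

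Section 3 defines the primary and secondary endpoints as changes from this baseline to day 180. Sections 9.4.2 and 9.4.3 compare the changes between arms and also enter the baseline score in the mixed model.

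On the run-in, 5.4 begins: "Screen failures are defined as participants who consent to participate in this study but are not subsequently assigned to the study intervention". The sentence then offers a second alternative, not having entered the study. The section goes on to count as screen failures people whose eligibility changes during run-in. Section 6.2 says: "Participants who are unable to successfully complete the run-in period will be terminated from the study and noted as a screen failure". Section 7.1 replaces people who were randomised but did not finish run-in. Section 9.3 promises an intention-to-treat analysis however long a person took part.

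**The concern.** A score recorded before allocation has the same expected value in both arms, so subtracting it or adjusting for it cannot bias the comparison. A self-report given after allocation, by someone who may know the arm, loses that guarantee. The scores at issue are subjective, and they are the primary and both secondary measures.

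The direction cannot be predicted. A baseline reported too high in the JITAI arm would inflate the apparent improvement, and one reported too low would hide a real effect. The baseline t-tests planned in 9.4.4 would not reliably show a shift of this kind (step 5 of the working).

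The early randomisation also sits badly with the run-in rules. People who already have an arm are labelled screen failures, a term 5.4 defines in part by not having been assigned.

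**Working it through.** **1. The plan's own figures.** Section 9.2 uses a difference of 4.0, two-sided alpha 0.05, 80% power, and SDs of 9.66 (strain), 9.79 (depression) and 9.53 (anxiety). With n per arm = 2(1.960 + 0.842)²SD²/4.0²:

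- strain: 2 × 7.849 × 93.32/16 = 91.6, so 92
- depression: 2 × 7.849 × 95.84/16 = 94.0 (just above 94), so 95
- anxiety: 2 × 7.849 × 90.82/16 = 89.1, so 90

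All three match. The exact t-test gives 93, 96 and 91. The order of baseline and randomisation enters none of these inputs.

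**2. Bias formulas.** Suppose knowing the arm adds d points to the JITAI baseline report and there is no true effect. Let rho be the correlation between baseline and day 180, with equal variances. Biases are given in absolute size.

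| Contrast | Shift gone by day 180 | Shift still present at day 180 |
|---|---|---|
| Change score | d | d − d = 0 |
| Baseline-adjusted | about rho × d | about (1 − rho) × d |
| Day-180 score alone | 0 | d |

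The documents give no value for d; 0.5, 1 and 2 T-score points are assumed. Section 9.2 gives rho from 0.4 to 0.8, but for the exploratory calculation only. Over that range, rho × d is 0.2–0.4, 0.4–0.8 and 0.8–1.6 points.

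**3. Type I error of the change-score contrast, shift gone by day 180.** Take 9.66 as the SD of change, as 9.2 does. SE = 9.66 × √(2/n), and P(reject) = Φ(d/SE − 1.96) + Φ(−d/SE − 1.96). At 140 per arm (the maximum in 1.1), SE = 9.66 × √(2/140) = 1.155. For d = 1, d/SE = 0.866, giving 0.137 + 0.002 = 0.139.

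| n per arm | d = 0.5 | d = 1 | d = 2 |
|---|---|---|---|
| 120 (240/2; close to 140 less 15% attrition, 119) | 0.069 | 0.126 | 0.361 |
| 140 | 0.072 | 0.139 | 0.410 |

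If 9.66 is instead the SD of a single score, the SD of change is 9.66 × √(2(1 − rho)), from 10.58 at rho 0.4 to 6.11 at rho 0.8. At 140 per arm and d = 1, type I error is then 0.124 to 0.278.

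**4. Other consequences at 140 per arm.** With baseline adjustment and d = 1, SE = 9.66 × √(1 − rho²) × √(2/140). Type I error is 0.067 at rho 0.4 and 0.211 at rho 0.8, so adjustment reduces the bias without removing it. If instead the shift works against a true 4-point effect, the change-score contrast has power 0.86, 0.74 and 0.41 for d of 0.5, 1 and 2.

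**5. Would the baseline table show it?** With a baseline SD of 9.66 and 140 per arm, the arithmetic is that of step 3. A baseline t-test has about 14% power to detect a 1-point shift and 41% for 2 points.

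**The case against.** The strongest reply is that the documents show an opportunity for bias but no bias. They give no evidence of a shift, no size and no direction, and zero is possible. That stands: every value of d above is an assumption.

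Several stronger readings are tempting, and the documents do not support them.

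- A reader might infer that JITAI participants have had their arm-specific explanation before they complete the baseline survey. In the 6.2 list, registration is the first item and that explanation the fifth, and the survey prompt follows registration, so the survey could come first. The text does not settle it. The schema and Schedule of Activities content was not available in the text examined and might.
- A reader might infer that the damage cannot be undone in analysis. It survives both planned analyses if the shift has gone by day 180. A comparison of day-180 scores without baseline would be free of a shift confined to baseline. If the shift persists, it cancels in the change score.
- A reader might infer that run-in failures are dropped from the analysis. No section says so. Section 7.1 says they are replaced, 9.3 promises intention-to-treat, and 10.1.3 retains the data of people who withdraw. The second alternative in the 5.4 definition also softens the conflict. What remains is a label that does not fit people already randomised, and an analysis status left unstated.

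None of this answers the main point: 4.1 and 8.1.2 both place allocation before baseline, and nothing keeps the arm from the participant.

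**Conclusion.** The point holds as a bias risk built into the order of events, of unknown size and direction. It rests on the sequence stated in 4.1 and 8.1.2, the absence of any described blinding, and the double use of the self-reported baseline in 9.4.2 and 9.4.3. The type I error figures of about 0.07, 0.14 and 0.41 show sensitivity only. They assume d, a shift that has gone by day 180, an SD of change of 9.66 and 140 per arm. Expressing an assumed d as a share of the 4-point target would turn a chosen input into an apparent estimate.

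The run-in matter is a separate inconsistency among 5.4, 6.2, 7.1 and 9.3. It needs reconciling, but it is not evidence of exclusion after randomisation.

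**What to change.** **Future enrolees.** Reword 4.1 and 8.1.2 so that the baseline HRQOL surveys are completed after consent, before the site randomisation list is opened and before any arm-specific explanation. This changes wording and task order and leaves the required numbers at 92, 95 and 90 per arm. The surveys are prompted after app registration, so registration would also have to precede allocation. The documents do not say whether the access code carries the arm, and this needs checking.

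**People already enrolled.** Record, as far as site records allow, the order of allocation, explanation and survey for each person. Add a sensitivity analysis of day-180 scores without baseline, for strain, anxiety and depression. If 9.66 is the SD of a single strain score, the plan's own 92 per arm gives that analysis 80% power for 4 points on strain. It does not protect against a reporting shift that lasts to day 180, so it should be read beside the change-score result.

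**Run-in failures.** Reconcile 5.4, 6.2 and 7.1 with 9.3 by stating that anyone randomised who does not complete run-in stays in the participant flow and in the intention-to-treat set, whether or not replaced.

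**Cost.** The reorder helps only people not yet enrolled. The amendment history shows enrolment under way well before version 4.0, and the number still to enrol is not stated. The trial would have two baseline procedures, so which one each participant followed should be recorded.

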8.1.3 DEMOGRAPHICS & CHARACTERIZATION

All participants will complete a series of surveys designed to characterize the sample with respect to demographics, caregiving experiences, and usual coping or management strategies.

- Participant Demographics. A study-designed form will be used to capture demographic data including age, gender, race, ethnicity, education, marital status, work status, COVID history/status, care partner data, care recipient data, etc. Administration time for this assessment is ~5-10 minutes.
- Medical History, Medications, Treatments, COVID Questionnaire. Study designed forms will be used to capture medical history and current treatments/management strategies (medication and non-medication – e.g., exercise, mindfulness) and COVID history. Administration time for this assessment is 10 minutes.
- Caregiver Appraisal Scale (CAS). The CAS assesses positive and negative aspects of the caregiving role. Four separate subdomain scores (perceived burden, caregiver relationship satisfaction, caregiving ideology, and caregiving mastery) can be calculated; higher scores indicating better functioning. Administration time for this 47-item measure is ~5-10 minutes.
- Mayo-Portland Adaptability Inventory- Fourth Edition (MPAI-4). The MPAI-4 is a 35-item proxy-report measure designed to assess functional ability for persons with TBI. Higher scores indicate poorer functional ability. The administration time for this measure is ~5-10 minutes.
- Posttraumatic Stress Disorder Checklist for DSM-5 (PCL-5). This version of the PCL-5 has been adapted for the proxy (in this study, the care partner is the proxy) assessment of posttraumatic stress disorder (PTSD) symptoms in the person with TBI. The PCL-5 is a 20-item measure that assesses the 20 symptoms of PTSD defined by the Diagnostic and Statistical Manual of Mental Disorders, 5th edition (DSM–5). A total symptom severity score, as well as 5 cluster scores can be

NIH Behavioral and Social Intervention Clinical Trial Protocol Template v3.0 - 20180827

obtained from this measure; higher scores indicate more PTSD symptomatology. Administration time for this 20-item measure is ~5-10 minutes.

- Supervision Rating Scale (SRS). This is a single rating that the caregiver provides about the overall amount of “supervision” that the person with TBI receives. Ratings range from 1-13; higher ratings indicate greater levels of required supervision. Administration time is ~2 minutes.
- Care Recipient Medical Record Information. Study staff will complete a CRF with information about the person with TBI for whom the care partner is providing care (e.g., time since diagnosis, details of diagnosis, disease stage/severity, imaging findings etc.). This data will be entered into the study database by study staff.

8.1.4 FITBIT® AND CAREQOL APP

Participants will be taught how to install both the Fitbit® and CareQOL apps onto their personal mobile devices. Participants will also be taught how to create and login to the necessary accounts. See section 6.2 for details regarding participant education.

- The study team will provide an access code for login to the CareQOL app.
- Participants will use a user id and personal email address of their choosing for their Fitbit® account.
- Data collected from the Fitbit® will be securely transmitted to the CareQOL app by user authentication token, which is comprised of a random series of characters that is used to securely query for user activity data.
- Participants will view their Fitbit® sleep and step-count data through the CareQOL app, though there are not restrictions on them also viewing the information in the Fitbit® app.

8.1.4.1 FITBIT®

All participants will don a wrist-worn Fitbit® with heart rate recording capabilities for the duration of the 10-day run-in period and 6-month (180 day) home monitoring period to monitor activity and sleep. While we intend to use the Fitbit Inspire HR®, we reserve the option to adopt a comparable device in the event of supply limitations or changes to the product line as long as there is minimal impact on the intervention delivery or primary outcome data integrity.

- Participants may use a personal Fitbit® if it has comparable features.
- Participants are expected to wear the Fitbit® continuously except for when charging and uploading data.
- Participants are expected to sync the Fitbit® daily.

8.1.4.2 CAREQOL APP

The study app (CareQOL) is the participant-facing platform for all daily, monthly and follow-up assessments, for viewing sleep and step count data from the Fitbit®, and for intervention delivery. After the home monitoring period is over (e.g. after the 6-month [180 day] assessment), the app will go into an “assessment only” mode during which only the +3 month (270 day) and +6-month (360 day) follow-up assessments will be activated. The daily and monthly assessments, the link with the Fitbit®, and intervention delivery will cease after the home monitoring period has elapsed.

8.1.4.3 RUN-IN HOME MONITORING PERIOD

A 10-day run-in period will follow the baseline assessment. This period is to allow shipping time of the Fitbit® and provide the participant time to familiarize themselves with the study technology (Fitbit®,

CareQOL app) and procedures. This period will also allow the study team to troubleshoot any potential barriers or issues that arise before the official start of the 6-month (180 day) home monitoring period. It also allows for data collection that can be used to inform the intervention messages once the home monitoring period begins.

8.1.5 HRQOL ASSESSMENT

Participants will complete a battery of HRQOL surveys; some will be administered daily and be used to drive the intervention, and others will be administered at baseline, monthly and during follow-up. The individual survey administration schedule is shown in the Table, and descriptions are provided below.

Table: HRQOL Assessment Schedule

	Baseline	Daily*	1m-5m (30, 60, 90, 120, 150d)	6m (180d)	+3m (270d) F/U	+6m (360d) F/U
Caregiver Strain SF	X		X	X	X	X
Caregiver-Specific Anxiety SF	X		X	X	X	X
Sleep-Related Impairment SF	X		X	X	X	X
Fatigue SF	X		X	X	X	X
Anxiety SF	X		X	X	X	X
Depression SF	X		X	X	X	X
Anger SF	X		X	X	X	X
Self-Efficacy SF	X		X	X	X	X
Positive Affect & Well-Being SF	X		X	X	X	X
Perceived Stress	X		X	X	X	X
Ability to Participate in Social Roles & Activities SF	X		X	X	X	X
Global Health	X		X	X	X	X
COVID HRQOL	X		X	X	X	X
Single-item Caregiver Strain		X				
Single-item Anxiety		X				
Single-item Depression		X				
MedHistory/Medications/Treatment/COVID	X		3m (90d)	X	X	X
AE/Status Update			3m (90d)	X	X	X
Feasibility				X		
*Daily surveys will be administered through the Run-in and 6-month home monitoring periods.						

- TBI-CareQOL Caregiver Strain Short Form (SF). TBI-CareQOL Caregiver Strain assesses

- perceived feelings of feeling overwhelmed, stressed and “beat-down” related to the care partner role. This measure is scored on a *T* metric (M = 50; SD = 10). Higher scores indicate more strain. The administration time for this measure is ~1 minute.
- TBI-CareQOL Caregiver-Specific Anxiety SF. TBI-CareQOL Caregiver-Specific Anxiety assesses perceived feelings of worry and anxiety specific to the safety, health, and future well-being of the person with TBI. This measure is scored on a *T* metric (M = 50; SD = 10). Higher scores indicate more anxiety. The administration time for this measure is ~1 minute.
 - PROMIS Sleep-Related Impairment SF. PROMIS Sleep-Related Impairment evaluates the effect of poor sleep on daytime functioning. This measure is scored on a *T* metric (M = 50; SD = 10). Higher scores indicate more sleep-related impairment. Administration time for this measure is ~1 minute.
 - PROMIS Fatigue SF. PROMIS Fatigue evaluates self-reported symptoms of fatigue, ranging from mild subjective feelings of tiredness to overwhelming exhaustion that may decrease one’s ability to perform activities of daily living. This measure is scored on a *T* metric (M = 50; SD = 10). Higher scores indicate more fatigue. Administration time for this measure is ~1 minute.
 - PROMIS Anxiety SF. PROMIS Anxiety assesses self-reported feelings of fear, anxiety and hyperarousal. This measure is scored on a *T* metric (M = 50; SD = 10). Higher scores indicate more anxiety. Administration time for this measure is ~1 minute.
 - PROMIS Depression SF. PROMIS Depression assesses self-reported feelings of sadness and worthlessness. This measure is scored on a *T* metric (M = 50; SD = 10). Higher scores indicate more depression. Administration time for this measure is ~1 minute.
 - PROMIS Anger SF. PROMIS Anger assesses self-reported feelings of irritability and frustration. This measure is scored on a *T* metric (M = 50; SD = 10). Higher scores indicate more anger. Administration time for this measure is ~1 minute.
 - NIH Toolbox Self-Efficacy. NIH Toolbox Self-Efficacy assesses self-reported confidence in the ability to successfully perform specific tasks or behaviors related to one’s overall functioning. This measure is scored on a *T* metric (M = 50; SD = 10). Higher scores indicate more self-efficacy. Administration time for this measure is ~1 minute.
 - Neuro-QoL Positive Affect & Well-Being SF. Neuro-QoL Positive Affect and Well-Being assesses parts of an individual’s life that are related to overall life meaning and purpose, well-being and satisfaction. This measure is scored on a *T* metric (M = 50; SD = 10). Higher scores indicate greater satisfaction. Administration time is ~1 minute.
 - NIH Toolbox Perceived Stress SF. NIH Toolbox Perceived Stress is a self-report measure designed to assess an individual’s feelings about the nature of events and individual coping resources. This measure is scored on a *T* metric (M = 50; SD = 10). Higher scores indicate more perceived stress. Administration time is ~1 minute.
 - PROMIS Ability to Participate in Social Roles and Activities SF. PROMIS Ability to Participate in Social Roles and Activities assesses involvement in one’s ability to participate in usual social roles and activities. This measure is scored on a *T* metric (M = 50; SD = 10). Higher scores indicate more ability to participate. Administration time is ~1 minute.
 - PROMIS Global Health v1.2. This 10-item patient-reported outcome measure assesses overall physical, mental, and social health. This measure is scored on a *T* metric (M = 50; SD = 10); separate scores are generated for physical and mental health. Higher scores indicate better health. The administration time for this measure is ~3 minutes.

- COVID HRQOL. This 1-item patient-reported outcome measure asks how concerned the participant is about COVID-19 from 0 – 10. The administration time for this measure is less than 1 minute.

